10.5 Appendix 5: Graft Versus Host Disease Scales

Table 5 MAGIC Criteria for Staging and Grading of Acute Graft Versus Host Disease

Stage	Skin (Active Erythema Only)	Liver (Bilirubin)	Upper GI	Lower GI (Stool Output/Day)
0	No active (erythematous) GVHD rash	<2 mg/dL	No or intermittent nausea, vomiting, or anorexia	Adult: <500 mL/day or <3 episodes/day. Child: <10 mL/kg per day or <4 episodes/day.
1	Maculopapular rash <25% BSA	2-3 mg/dL	Persistent nausea, vomiting, or anorexia	Adult: 500-999 mL/day or 3-4 episodes/day. Child: 10-19.9 mL/kg per day or 4-6 episodes/day.
2	Maculopapular rash 25%-50% BSA	3.1-6 mg/dL	-	Adult: 1000-1500 mL/day or 5-7 episodes/day. Child: 20-30 mL/kg per day or 7-10 episodes/day.
3	Maculopapular rash >50% BSA	6.1-15 mg/dL	-	Adult: >1500 mL/day or >7 episodes/day. Child: >30 mL/kg per day or >10 episodes/day.
4	Generalized erythroderma (>50% BSA) plus bullous formation and desquamation >5% BSA	>15 mg/dL	-	Severe abdominal pain with or without ileus or grossly bloody stool (regardless of stool volume).

Overall clinical grade (based on most severe target organ involvement):

Grade 0: No Stage 1 to 4 of any organ.

Grade I: Stage 1 to 2 skin without liver, upper GI, or lower GI involvement.

Grade II: Stage 3 rash and/or Stage 1 liver and/or Stage 1 upper GI and/or Stage 1 lower GI.

Grade III: Stage 2 to 3 liver and/or Stage 2 to 3 lower GI, with Stage 0 to 3 skin and/or Stage 0 to 1 upper GI.

Grade IV: Stage 4 skin, liver, or lower GI involvement, with Stage 0 to 1 upper GI.

Abbreviations: BSA = body surface area; GI = gastrointestinal; GVHD = graft versus host disease; MAGIC = Mount Sinai Acute GVHD International Consortium

Source: Harris AC, Young R, Devine S, et al. International, multicenter standardization of acute graft-versus-host disease clinical data collection: a report from the Mount Sinai Acute GVHD International Consortium. Biol Blood Marrow Transplant. 2016;22(1):4-10.

Table 6 Response Definitions for Acute Graft Versus Host Disease

Response Term	Definition
CR	Complete resolution of all signs and symptoms of GVHD in all organs without intervening salvage therapies.
PR	Improvement of 1 stage in 1 or more organs involved by GVHD without progression in others.
Mixed response	Improvement in at least 1 involved organ with progression or newly developed GVHD in 1 or more organs.
Progression	Worsening in 1 or more organs by 1 or more stage without improvement in any involved organ.
NR	No improvement or deterioration in any organ within 14 days of therapy initiation.

Abbreviations: CR = complete response; GVHD = graft versus host disease; NR = no response; PR = partial response.
Source: Center for International Blood & Marrow Transplant Research (CIBMTR). Clinical trial endpoints for patients with acute GVHD. 2009. <https://www.cibmtr.org/Meetings/Materials/GVHDworkshop/pages/index.aspx>.

10.6 Appendix 6: Cytokine Release Syndrome Scale

Table 7 Cytokine Release Syndrome Scale

CRS Parameter	Grade	1	2	3	4
Fever ^[1]		≥38.0°C	≥38.0°C	≥38.0°C	≥38.0°C
With					
Hypotension	None	Not requiring vasopressors	Requiring vasopressors with or without vasopressin	Requiring multiple vasopressors (excluding vasopressin)	
And/or ^[2]					
Hypoxia	None	Requiring lowflow nasal cannula (oxygen delivered at ≤6 L/minute) or blowby	Requiring highflow nasal cannula (oxygen delivered at >6 L/minute), facemask, nonrebreather mask, or Venturi mask	Requiring positive pressure (eg, CPAP, BiPAP, intubation, mechanical ventilation)	

Note: Organ toxicities associated with CRS may be graded according to CTCAE v5.0 but they do not influence CRS grading.

[figure not shown]
Note: Grade 5 CRS is defined as death due to CRS, in which another cause is not the principle factor leading to the outcome.

- 1 Fever is defined as temperature ≥38.0°C not attributable to any other cause. In patients who have CRS and then receive antipyretic or anticytokine therapy such as tocilizumab or steroids, fever is no longer required to grade subsequent CRS severity. In this case, CRS grading is driven by hypotension and/or hypoxia.
- 2 CRS grade is determined by the more severe event: hypotension or hypoxia not attributable to any other cause. For example, a patient with temperature of 39.5°C, hypotension requiring 1 vasopressor, and hypoxia requiring low-flow nasal cannula is classified as grade 3 CRS.

Abbreviations: BiPAP = bilevel positive airway pressure; CPAP = continuous positive airway pressure; CRS = cytokine release syndrome; CTCAE = Common Terminology Criteria for Adverse Events.

Source: Lee DW, Santomasso BD, Locke FL, et al. ASTCT consensus grading for cytokine release syndrome and neurologic toxicity associated with immune effector cells. Biol Blood Marrow Transplant. 2019;25(4):625-638.

10.7 Appendix 7: Modification of Immunosuppression

NOTE: *Viral load determinations that would lead to changes in immunosuppression (red boxes) should be repeated immediately upon receipt to confirm that action should be taken as indicated.

- a If MMF has already been reduced or discontinued more than 28 days prior, proceed to the next step in the algorithm. Other variations from the algorithm require consultation with, and approval by, the Sponsor's Medical Monitor.
- b Triple Immunosuppression: low-dose oral steroids, MMF, and calcineurin inhibitor.
- c Double Immunosuppression: MMF and calcineurin inhibitor.

Abbreviations: AST = American Society of Transplantation; KDIGO = Kidney Disease: Improving Global Outcomes; MMF = mycophenolate mofetil; PCR = polymerase chain reaction; PI = Principal Investigator (ie, Investigator); Q = very; VL = viral load

| Abbreviation | Definition |
|--------------|--|
| AdV | Adenovirus |
| AE | Adverse Event |
| AESI | Adverse Event of Special Interest |
| ALT | Alanine Aminotransferase |
| ALP | Alkaline Phosphatase |
| ALVR105 | Posoleucel (formerly Viralym-M) |
| AST | Aspartate aminotransferase |
| ATC | Anatomical Therapeutic Chemical |
| BKV | BK Virus |
| CI | Confidence Interval |
| CMV | Cytomegalovirus |
| CRF | Case Report Form |
| CRS | Cytokine Release Syndrome |
| CTCAE | Common Terminology Criteria for Adverse Events |
| DNA | Deoxyribonucleic acid |
| DSMB | Data Safety Monitoring Board |
| EBV | Epstein-Barr Virus |
| ECG | Electrocardiograms |
| eGFR | estimated Glomerular Filtration Rate |
| GVHD | Graft vs Host Disease |
| HBV | Hepatitis B Virus |
| HCV | Hepatitis C Virus |
| HHV-6 | Human Herpesvirus 6 |
| HIV | Human Immunodeficiency Virus |
| HLA | Human Leukocyte Antigen |
| IFN | Interferon |
| IQR | Interquartile Range |
| ITT | Intent-to-Treat |
| IV | Intravenous(ly) |
| JCV | JC Virus |
| LOCF | Last Observation Carried Forward |
| MDRD | Modified Dose in Renal Disease |
| MedDRA | Medical Dictionary for Regulatory Activities |
| NCI | National Cancer Institute |
| PSL | Posoleucel or ALVR105 (formerly Viralym-M) |
| SAE | Serious Adverse Event |
| SAP | Statistical Analysis Plan |
| SD | Standard Deviation |
| TEAE | Treatment-Emergent Adverse Event |
| TESAE | Treatment-Emergent Serious Adverse Event |
| ULN | Upper Limit of Normal |
| Viralym-M | Posoleucel or ALVR105 |
| WHO | World Health Organization |

1 INTRODUCTION

The purpose of this Statistical Analysis Plan (SAP) is to provide a description of the statistical methods to be implemented for the analysis of data from Study P-105-201 under Protocol Version 4.0, 30 Sep 2021. The SAP will be finalized prior to database lock. Any deviations from the SAP after database lock will be documented in the final Clinical Study Report (CSR).

2 STUDY OVERVIEW

2.1 Study Objectives

2.1.1 Primary Objective

The primary objective is to compare the safety and tolerability of posoleucel (PSL, ALVR105, formerly Viralym-M) to placebo in kidney transplant recipients.

2.1.2 Secondary Objectives

The key secondary objective is to assess the overall efficacy of PSL to suppress BK viral load compared with placebo.

The other secondary objective is to compare the relative efficacy of different dosing regimens of PSL to suppress BK viral load versus placebo.

2.1.3 Exploratory Objectives

The exploratory objectives include comparisons of the following in recipients of PSL and in patients receiving placebo:

- To assess change in estimated glomerular filtration rate (eGFR) over 24 weeks in recipients of PSL versus placebo
- To identify changes in donor-specific anti-human leukocyte antigen (anti-HLA) antibodies in recipients of PSL versus placebo
- To determine the proportion of patients with resolution of BK viremia at 8 weeks post virus-specific T cell infusion
- To assess kidney allograft survival at 24 weeks
- To assess the incidence of recrudescent or new infections with target viruses (including cytomegalovirus [CMV]), but principally BKV
- To determine whether patients with initially low BK viral load (ie, <10,000 copies/mL) can be prevented from developing viremia \geq 10,000 copies/mL that leads to new or increased immunosuppression reduction
- To determine whether patients with initially low BK viral load (ie, <10,000 copies/mL) in the investigational arm(s) develop lower viral loads than the placebo arm

2.2 Study Design

2.2.1 Overview

This is a Phase 2, multicenter, randomized, double-blind, placebo-controlled, multiple dosing interval, 2-period study of the safety, tolerability and efficacy of adoptively transferred PSL virus-specific T cells in kidney transplant recipients with BK viremia.

This study is comprised of 2 periods. Period 1 includes a 2-week window for screening assessments followed by a 12-week treatment period for eligible patients. Period 2 (consists of a 12-week) follow-up. Overall, the total duration of patient participation in the study is approximately 26 weeks (2 weeks for screening, 12 weeks of treatment, and 12 weeks of follow-up).

Patients who meet all of the inclusion criteria and none of the exclusion criteria will be enrolled into the study and randomized to receive PSL or placebo infusions. Patients will be stratifie [REDACTED]

[REDACTED] atients will be monitored following randomization for safety, BK viral load, renal function, and immune function, including modification of immunosuppression reduction. Patients will be monitored following randomization for safety, BK viral load, renal function, and immune function, including modification of immunosuppression reduction.

Patients will receive infusions of either PSL or placebo for 12 weeks. [REDACTED]

[REDACTED] All infusions will be administered IV (via peripheral or central line) over approximately [REDACTED] as a slow push. Patients will receive the same dose for all infusions.

The study will consist of 3 treatment arms. To maintain the blind, all patients will receive an infusion (either PSL or placebo) weekly for the first 3 weeks of the dosing period, followed by every other week dosing for the remaining 9 weeks. The treatment arms and associated infusions are as follows:

[REDACTED]

Administrative interim analyses are planned for the study as described in Section 3.7. The Sponsor's study team and Investigators will remain blinded to individual patient data during and after the administrative interim analyses.

After the first 3 doses, patients who have undetectable BK plasma viral load at 2 or more consecutive assessments at least 2 weeks apart will discontinue PSL infusions. If a patient's viral load becomes undetectable, such a patient may be followed every 14 days for study evaluations as per the Schedule of Activities. Patients will not be permitted to receive a subsequent infusion of PSL if they develop new onset graft vs host disease (GVHD) \geq Stage 1 or cytokine release syndrome (CRS) > Grade 2 at the proposed time for infusion of any subsequent dose.

A summary of study design is shown in [Figure 1](#).

2.2.2 *Study Drug*

PSL is a third-party, donor-derived, "off-the-shelf," virus-specific T cell product with specificity for BKV, AdV, CMV, EBV, and HHV-6 (with additional cross-reactive specificity for JCV) that is cryopreserved and ready for immediate use. Cryopreservation media (without cells) will serve as the placebo and will be identical in volume and appearance when administered.

2.2.3 *Sample Size Determination*

No formal sample size determination was made for this study, whose primary endpoint is safety and tolerability. Approximately 60 patients will be randomized at approximately 38 clinical sites. Patients (n=20 in each arm) will be randomized to receive PSL (administered at a dose interval of every 14 or 28 days after 3 initial weekly doses) or placebo.

Patients will be stratified [REDACTED]

[REDACTED] A minimum of 6 patients must be enrolled in each stratum, but the remaining patients can be enrolled in either stratum.

Figure 1. Study Flow Chart

b Administrative interim analysis #1 will be performed by the Sponsor when 12 patients in Stratum 1 have completed 8 weeks in the study. Administrative interim analysis #2 will be performed when 30 patients have completed 8 weeks in the study. Interim analyses may be omitted or added at the discretion of the Sponsor to allow for long term planning, and to assess ending the study or either arm early.

Abbreviations: BKV=BK virus; Q=every; S/P=status post

2.3 Study Endpoints

2.3.1 Primary Endpoint

The primary endpoint is safety and tolerability assessed by treatment-emergent adverse events (TEAEs) and changes in vital signs, physical examinations, clinical laboratory assessments, and ECGs in kidney transplant recipients.

2.3.2 Secondary Efficacy Endpoints

The key secondary endpoint is change in BK viremia in patients receiving PSL compared to patients receiving placebo.

The other secondary efficacy endpoint is change in BK viremia in patients receiving different dosing regimens of PSL or placebo.

The comparison will be based on quantitation of plasma BK viral load performed at the central laboratory. Viral load will be quantitated using polymerase chain reaction assays.

2.3.3 Exploratory Efficacy Endpoints

The exploratory efficacy endpoints include comparison between results in patients receiving PSL versus placebo for the following:

- Change in eGFR by Modified Dose in Renal Disease (MDRD) formula.
- Changes from baseline in levels of donor-specific anti-HLA antibodies.

- Proportion of patients with resolution of BK viremia at 8 weeks post virus-specific T cell infusion.
- Proportion of patients with eGFR >20 mL/min at 24 weeks.
- Incidence of new target viral infections or recrudescent infections (i.e., BKV, CMV, EBV, AdV, JCV, and/or HHV-6) as defined by onset of viremia and/or the presence of associated symptoms relative to baseline.
- Length of BKV remission (i.e., time from clearance of BK viremia to reappearance of BK viremia (plasma viral load >156 copies/mL \times 2 measures that are at least 2 weeks apart) or end of study).
- Number of patients with screening BK viremia < 10,000 copies/mL who develop BK viremia \geq 10,000 copies/mL (sustained or non-sustained) or who experience a medically significant event that leads to changes in immunosuppression reduction.
- The absolute viral load in patients in the investigational arms versus that in patients in the placebo arm with screening BK viremia <10,000 copies/mL.

2.3.4 Other Endpoints

The other endpoints include the following:

- Frequency and severity (adjudicated Banff classification) of biopsy-proven acute allograft rejection in recipients of PSL versus placebo.
- Number of patients in the investigational arms with polyomavirus haufen in the urine as compared to the placebo arm.
- Quantification of IFN- γ (+) T cells specific for BK virus in patients in the investigational arms as compared to the placebo arm.
- Levels of (virus-specific T cell) donor T cell deoxyribonucleic acid (DNA) as compared to patient T cell DNA in peripheral blood.
- Time to resolution of non-BK target viral infections (i.e., associated signs, symptoms, and presence/absence of HHV-6, EBV, JCV, and/or AdV viremia) present at the time of randomization.
- Use of immunosuppressive agents, including specific immunosuppressive agents used, doses, and any changes in dose.
- Number of hospitalizations/re-hospitalizations for any reason and number of days.
- Incidence and duration of use of any other antiviral therapies during the study.
- Time to death (from any cause) from the time of randomization.
- Number of patients with kidney injury requiring hemodialysis.
- Rate of decline of BK viremia in recipients of PSL using different dosing intervals versus that in patients receiving placebo.

- Assessment of renal function (eGFR estimated by the creatinine-cystatin C method reported by central lab).

The biomarker data, including IFN- γ (+) T cells specific for BK virus, polyomavirus haufen in the urine, and T cell receptor sequencing data will not be analyzed in this SAP but reported separately.

2.3.5 Safety Endpoints

Safety endpoints include treatment-emergent adverse events (TEAEs), change in vital signs, physical examination findings, clinical laboratory evaluations (clinical chemistry, hematology, urinalysis, pregnancy testing and other screening tests), and 12-lead Electrocardiograms (ECGs).

The adverse events of special interest (AESI) include infusion-related AEs, GVHD, and CRS. Grading criteria for GVHD and CRS can be found in Appendix 5 (Protocol Section 10.5) and Appendix 6 (Protocol Section 10.6), respectively. These AESIs will be reviewed by the DSMB as per the DSMB Charter.

3 STATISTICAL METHODOLOGY

3.1 General Considerations

3.1.1 Study Day

Analysis day will be calculated from the date of first dose of study drug, as analysis day = actual visit date – first dose date + 1. The day of the first dose of study drug will be Day 1, and the day immediately before and after Day 1 will be Day -1 and Day 2.

3.1.2 Analysis Visits

Subject visits might not occur on protocol-specified days. Therefore, for the purpose of analysis, all scheduled, unscheduled, and early termination visits will be assigned to analysis visits according to the analysis windows ([Appendix 1](#)) based on study days. If there is more than 1 assessment in an analysis window, the assessment closest to the target day will be used in the analysis. If there are 2 assessments in a window equidistant from the target day, the later assessment will be used in the analysis.

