18. Patients will be monitored closely and must remain in the clinic for \geq 1 hour after the end of each infusion. Vital signs, including body temperature, heart rate, respiration rate, and blood pressure, will be measured within 30 minutes prior to infusion, at the end of the infusion, and at 15, 30, 45, and 60 minutes after the end of the infusion. A \pm 5 minute window is permitted for all vital sign measurements. Patients must also remain on continuous pulse oximetry for \geq 30 minutes after the end of the infusion. Post-infusion monitoring should be completed for all infusions of study treatment.
19. Blood will be collected into a cell separation tube and processed to generate a PBMC fraction and a plasma fraction. These fractions will be cryopreserved for potential future evaluation of virus-specific T cell immune function/virus-specific T cell persistence and for potential future evaluation of cytokines and/or other humoral markers of inflammation and/or immune function. In addition, a tube of whole blood will be collected for exploratory determination of virus-specific- T cell immune function in whole blood.
20. Blood will be obtained for (virus-specific T cell) donor DNA quantitation at Weeks 4, 12 and 24. Week 24 DNA may not be quantitated, depending on earlier results.
21. Week 24 procedures should be performed on any patient who terminates the study early before Week 24.
22. Serum will be screened for HIV, HBV and HCV antibodies with reflex nucleic acid testing of plasma.
23. Severity of Biopsy (for clinical indication) Proven Acute Rejection will be adjudicated by a blinded review via expert pathologists. No biopsies are required per the protocol.
24. Donor-specific antibody results should be derived from samples sent to the central laboratory.

Abbreviations: AdV = adenovirus; ALT = alanine aminotransferase; AST = aspartate aminotransferase; BKV = BK viremia; CBC = complete blood count; CMV = cytomegalovirus; CRS = cytokine release syndrome DNA = deoxyribonucleic acid; EBV = Epstein-Barr virus; ECG = electrocardiogram; ET = Early Termination Visit; FSH = follicle-stimulating hormone; GVHD = graft versus host disease; HBV = hepatitis B virus; HCV = hepatitis C virus; HIV = human immunodeficiency virus; HHV-6 = human herpesvirus 6; HLA = human leucocyte antigen; I/E = inclusion and exclusion; JCV = JC virus; LFT = liver function test; NA = not applicable; PBMC = peripheral blood mononuclear cell; PSL=psoleucel; SoA = Schedule of Activities

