APPENDIX A: SCHEDULE OF ACTIVITIES**Table 2: Schedule of Activities in Period 1 (Weeks -2 to 12)**

At the discretion of the Investigator, and with the exception of Weeks 8 and 12 (which must be conducted at the site), study visits for patients who have undetectable BK plasma viral load at 2 or more consecutive assessments at least 2 weeks apart after 3 doses may be conducted by a Sponsor-approved home health vendor in conjunction with a Sponsor-approved telehealth provider. These visits may be conducted via video or telephone call.

| Study Week | Weeks -2 to -1 | Day 1 | Week 1 | Week 2 | Week 4 | Week 6 | Week 8 | Week 10 | Week 12 |
|---|-------------------|-------------------|--------|------------------|-------------------|--------|-------------------|---------|-------------------|
| Study Day | -14 to -1 | 1 ^[1] | 8 | 15 | 29 | 43 | 57 | 71 | 85 |
| Visit Window (Days) | NA | NA | ±2 | ±3 | ±3 | ±3 | ±3 | ±3 | ±3 |
| Study Procedures | | | | | | | | | |
| Informed consent ^[2] | X | | | | | | | | |
| I/E criteria | X | X | | | | | | | |
| Demographics | X | | | | | | | | |
| Medical history | X | | | | | | | | |
| Prior & concomitant medications | X | X | X | X | X | X | X | X | X |
| Adverse events ^[3] | X | X | X | X | X | X | X | X | X |
| Complete physical examination ^[4] | X | X | | | | | | | X |
| Targeted physical examination ^[4] | | | X | X | X | X | X | X | |
| Weight and height ^[5] | X | X | | | X | | X | | X |
| Vital signs ^[6] | X | X | X | X | X | X | X | X | X |
| 12-lead ECG ^[7] | X | X ^[7] | | X ^[7] | | | | | |
| Documentation of HLA typing ^[8] | X | | | | | | | | |
| Clinical labs ^[9] | X | X | | X | X | X | X | X | X |
| Testing for HIV, HCV, and HBV ^[22] | X | | | | | | | | |
| BKV plasma viral load ^[10,11] | X | X | | X | X | X | X | X | X |
| Urine for biomarker ^[12] | | X | | | X | | X | | X |
| AdV, CMV, JCV, HHV-6 plasma, and EBV viral load ^[10] | | X | | | X | | X | | X |
| Pregnancy test | X ^[13] | X ^[14] | | | X ^[14] | | X ^[14] | | X ^[14] |
| FSH ^[15] | X | | | | | | | | |
| Randomization ^[16] | | X | | | | | | | |
| Provide patient cards | | X | | | | | | | |
| Study treatment administration ^[17] | | X | X | X | X | X | X | X | X |

| Study Week | Weeks -2 to -1 | Day 1 | Week 1 | Week 2 | Week 4 | Week 6 | Week 8 | Week 10 | Week 12 |
|---|-------------------|------------------|--------|--------|--------|--------|--------|---------|---------|

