| Study Day | -14 to -1 | 1 ^[1] | 8 | 15 | 29 | 43 | 57 | 71 | 85 |
| Visit Window (Days) | NA | NA | ±2 | ±3 | ±3 | ±3 | ±3 | ±3 | ±3 |
| Post infusion monitoring ^[18] | | X | X | X | X | X | X | X | X |
| Banked PBMCs for virus specific immunity ^[19] | X | | | X | X | X | X | | X |
| Blood for donor DNA ^[20] | | | | | X | | | | X |
| Kidney biopsy pathologic specimens for review (if clinically indicated) ^[23] | X | X | X | X | X | X | X | X | X |
| Donor-specific antibodies ^[24] | | X | | | | | | | X |

1. Unless noted otherwise, the Day 1 procedures must be performed within 96 hours of randomization and prior to study treatment administration.
2. Prior to conducting any study-related activities, written informed consent to participate in the study must be provided by the patient.
3. Adverse events will be monitored and documented from randomization through Week 24 in all patients.
4. Complete physical examinations require the patient to be at the site, and will include, at a minimum, assessments of the Cardiovascular, Respiratory, Gastrointestinal and Neurological systems. Targeted physical examinations or assessments will include careful skin examination for GVHD, and other aspects as clinically indicated.
5. Height and weight will be measured at screening; only weight will be measured at other specified later visits. For home visits, stated weight may be used.
6. Includes body temperature, blood pressure, heart rate, and respiration rate and will be measured after resting for 5 minutes. For visits with infusions, vital signs will be measured within 30 minutes prior to infusion, at the end of the infusion, and at 15, 30, 45, and 60 minutes after the end of the infusion. A ±5 minute window will be permitted for all vital sign assessments.
7. Performed within 1 hour after study treatment administration and at the end of study or early termination visit. ECGs will be obtained with the patient in a semi-supine position after a 5-minute rest.
8. The HLA type of the patient and their donor kidney will be obtained from the medical record.
9. CBC must include differential and LFTs must include alkaline phosphatase, bilirubin, AST, and ALT. Urinalysis must be performed.

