| Day 1/Baseline | 1 | 1 | 1 |
| Week 2 | 15 | 2 | 92 |
| Week 24 | 169 | >92 | |

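### ECGs taken at early exit or at unscheduled visits on Days 19 to 92 are left out of the windowed ECG summaries when a Week 2 ECG exists; other exit ECGs can be reported as Week 2 or Week 24 far from those days

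*SAP*

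**What the plan says.** Assignment to visits is set in SAP 3.1.2: "all scheduled, unscheduled, and early termination visits will be assigned to analysis visits according to the analysis windows". The selection rule follows: "If there is more than 1 assessment in an analysis window, the assessment closest to the target day will be used in the analysis". Ties are settled there too: "If there are 2 assessments in a window equidistant from the target day, the later assessment will be used in the analysis".

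For ECGs, SAP Appendix B Table 5 gives Day 1, a Week 2 window with target Day 15 running from Day 2 to Day 92, and an open-ended last row, "Week 24 | 169 | >92".

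An ECG at exit is expected. The schedule's footnote 21 (Protocol 1.3) says "Week 24 procedures should be performed on any patient who terminates the study early before Week 24", and the Week 24/ET column of Protocol Table 2 includes an ECG. Footnote 7, repeated in SAP Appendix A, describes the ECG as "Performed within 1 hour after study treatment administration and at the end of study or early termination visit". In Period 1 the schedule marks ECGs only at screening, Day 1 and Week 2 (Day 15 ± 3).

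SAP 3.5.4 summarises observed ECG values and changes from baseline descriptively, and lists all ECG parameters by patient with the investigator's interpretation. It plans no worst-value, last-value or early-termination summary. By contrast, SAP 3.5.2 tabulates the worst post-baseline laboratory grade against baseline.

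**The concern.** Infusion visits fall on Days 1, 8, 15, 29, 43, 57, 71 and 85. Scheduled post-dose ECGs follow only the Day 1 and Day 15 infusions, and the next scheduled ECG is at Day 169. An ECG near the Day 29 to 85 infusions can therefore exist only if a patient leaves the study or has an unscheduled recording.

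Those are the ECGs that a Week 2 window reaching to Day 92, combined with a closest-to-target rule, leaves out or relabels. ECG change is a named component of the primary endpoint (SAP 2.3.1), and Protocol 2.4.2 lists arrhythmia among the possible effects of infusion. The ECG table could thus omit a late on-treatment value that a safety reader would want to see, including from the tabulated minimum and maximum.

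**Working it through.** **Inputs.**
- ECG windows: Week 2 = Days 2 to 92, target 15; Week 24 = after Day 92, target 169 (SAP Appendix B Table 5).
- Scheduled Week 2 ECG: Day 15 ± 3, that is Days 12 to 18 (Protocol Table 1).
- Closest to target is used; a tie goes to the later assessment (SAP 3.1.2).
- Latest in-window Week 12 visit: 85 + 3 = Day 88.

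**The plan's own figure.** The Day 92 limit is the midpoint of the two targets: (15 + 169) / 2 = 92. Laboratory Week 12 is built the same way, ending at (85 + 113) / 2 = 99. The limit is therefore a convention applied consistently, not a typing error.

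**Distance comparison.** A scheduled Week 2 ECG is at most 3 days from target. An ECG on Day 19 is 19 − 15 = 4 days away, and any later one is further. So every exit or unscheduled ECG on Days 19 to 92 loses to an in-window Week 2 ECG. Since 88 < 92, this covers the whole remaining treatment period.

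**Enumeration of exit days through Day 92, for an exit after the Week 2 ECG.**

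| Week 2 ECG on | Possible exit days | Exit ECG used as Week 2 | Exit ECG left out |
|---|---|---|---|
| Day 12 | 80 | 6 (Days 13–18) | 74 |
| Day 13 | 79 | 4 (Days 14–17) | 75 |
| Day 14 | 78 | 2 (Days 15–16) | 76 |
| Day 15 | 77 | 0 | 77 |
| Day 16 | 76 | 0 | 76 |
| Day 17 | 75 | 0 | 75 |
| Day 18 | 74 | 0 | 74 |
| Not done | 91 (Days 2–92) | 91 | 0 |

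With a Week 2 ECG, an exit ECG is used only when the two are a few days apart. With none, the exit ECG is always kept but labelled Week 2, at worst 92 − 15 = 77 days after target.

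**Exit from Day 93.** The ECG goes to Week 24, where it is the only protocol-required ECG for that patient, so it is kept. At Day 93 it is 169 − 93 = 76 days before target.

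**Number of patients.** The documents give no dropout rate, so no count follows from them. As an assumption only: if 5% to 15% of 60 patients leave early and half of those leave by Day 92, then 60 × 0.05 × 0.5 = 1.5 and 60 × 0.15 × 0.5 = 4.5. That is about 2 to 5 exit ECGs left out or labelled Week 2, and a similar number labelled Week 24. Unscheduled ECGs in patients who stay in the study would add to this by an unknown amount.

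**The case against.** A reader might infer that the ECG summaries lose the patients who withdraw during treatment. The documents do not support that. A patient with a Week 2 ECG stays in the Week 2 row and loses only the later value. A patient without one is kept under the wrong label, and an exit after Day 92 is kept as Week 24.

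Further points on the other side:
- Stopping infusions is not leaving the study. Protocol 7.1 asks that such patients stay in follow-up, so they remain due for the Day 169 ECG. This stands and narrows the group with exit ECGs. It does not empty it: Protocol 7.2 allows withdrawal for adverse events, and Protocol 6.3 requires withdrawal after an investigator unblinds a patient.
- SAP 3.5.4 does not say that ECGs are summarised by visit; 3.5.3 does say so for vital signs. That use of Table 5 is an inference. It is the natural one, because ECG has its own window table. If it is not intended, 3.5.4 leaves the selection of ECGs undefined.
- The information is not lost. All ECGs are listed, and abnormalities that the investigator judges clinically significant are adverse events (Protocol 10.3.1) and enter the adverse-event tables. The primary assessment is qualitative, with no formal hypothesis test. This stands and limits the weight of the point. A listing is still not a comparison of treatment groups.
- The gap in scheduled ECGs between Week 2 and Week 24 comes from the protocol schedule, not from the windows. A few exit ECGs at arbitrary times after an infusion would not fill it. Moreover, one active arm receives PSL every 28 days (SAP 2.2.3) with placebo infusions in between, so not every infusion on Days 29 to 85 is PSL even in active patients. Both points stand.

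**Conclusion.** The point holds in a limited form. With an in-window Week 2 ECG, an early-termination or unscheduled ECG on Days 19 to 92 does not enter the windowed summaries. Without one, an exit ECG is reported as Week 2 up to Day 92. From Day 93 it is reported as Week 24, up to 76 days early. The effect is on individual values and labels in a descriptive table, not on whether patients are included.

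The conclusion assumes that the 3.5.4 summaries use the 3.1.2 analysis visits. The number affected is probably small and cannot be derived from the documents; the 2 to 5 shown above rests wholly on an assumed dropout rate. The documents do not support a claim that the safety conclusion would be biased by a known amount. The change is worth making because it is cheap, uses ECGs already collected, and concerns a component of the primary safety endpoint.

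**What to change.** In SAP 3.5.4 and Appendix B Table 5:

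1. Add an 'Early termination/last post-baseline' row to the ECG summaries, so that exit ECGs are always tabulated.
2. Add a worst post-baseline QTc summary (value and change from baseline) over all scheduled, unscheduled and exit ECGs, following the worst-value approach of 3.5.2.
3. Do not report exit ECGs far from target under the Week 2 or Week 24 label.
4. State in 3.5.4 whether ECG summaries are by analysis visit.

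Narrowing the windows alone is not a remedy. For example, ending Week 2 at Day 29 and starting Week 24 at Day 155 would leave Days 30 to 154 in no window and so remove exit ECGs on Days 93 to 154 that the SAP now keeps. If the windows are narrowed, the added rows must cover the days left outside them.

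The cost is SAP text and programming, with no new data and no change to patient care. The downside is a few extra rows with few patients in each.
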